7.1. Disposition of Patients/Subjects and Withdrawals

The number of subjects in each treatment group will be summarized. The number and percentage of subjects who complete the study and who screen fail will be summarized by treatment group. The reasons for screen failure will also be summarized. The number and percentage of subjects in the safety population will be summarized by treatment group.

All disposition information will be listed.

7.2. Protocol Violations and Deviations

Protocol deviations will be listed.

7.3. Demographics and Other Baseline Characteristics

Demographic variables collected in the VMDN-003 study such as age, gender, ethnicity, and race, and baseline characteristics such as height, weight, body mass index (BMI), baseline gabapentin/pregabalin use, and diabetes type will be summarized by treatment group and by treatment group within baseline gabapentin/pregabalin use. The gabapentin/pregabalin summary will be excluded from the subgroup tables.

Categorical variables, such as gender, ethnicity, race, baseline pregabalin/gabapentin use, and diabetes type will be summarized using frequencies and percentages. Continuous variables such as age, height, weight, and BMI will be summarized using mean, standard deviation (SD), median, minimum, and maximum.

8. Efficacy Analysis

Other variance-covariance structures selected from among compound symmetry, Toeplitz, and autoregressive (1) options will be substituted based on the lowest AIC if convergence problems arise.

The model will be run using the ITT population as well as the mITT population.

Similarly, a generalized linear mixed-effects model for repeated measures based on a logit link

function (hereinafter, the categorical Repeated Measures Model) will be used for comparing the percentage of subjects with a percent change in average 24-hour pain score of ≤ -50% (responder rate) between the two study treatment groups. The model will include treatment, visit, treatment-by-visit interaction, baseline use of gabapentin and/or pregabalin, and baseline average 24-hour pain scores as covariates with an unstructured variance-covariance matrix. The point estimates for the least-squares mean of the treatment difference (VM202 − Placebo) and the corresponding 95% confidence interval and p-value will be summarized.

The SAS code to be used to conduct the analysis is presented below:

PROC GLIMMIX DATA=work method=quad;

class usubjid trtp avisitn basemed;

MODEL critvar(event='Y') = trtp base avisitn basemed trtp*avisitn / DIST=binary LINK=LOGIT SOLUTION:

random INTERCEPT / SUBJECT=usubjid type=un;

Ismeans trtp *avisitn / diff cl;

RUN;

Where USUBJID: subject ID

TRTP: treatment

AVISITN: variable representing visits (Primary model will include the 3, 6, 9 and 12 month visits)

CHG: change in average pain score from baseline

BASE: baseline average pain score

BASEMED: a Y/N variable indicating if the subject took gabapentin/pregabalin at baseline.

CRITVAR: a Y/N variable indicating if the subject had at least a 50% reduction in baseline pain score from baseline at that visit

To derive the estimates comparing the 2 treatment arms for the change from day 270 to day 365, a contrast statement will be used.

Other variance-covariance structures selected from among compound symmetry, Toeplitz, and autoregressive (1) options will be substituted based on the lowest AIC if convergence problems arise.

The model will also be run comparing responder rates of 20%, 30%, 40%, 60%, and 70% reductions from baseline. Frequencies and percentages of subjects achieving those response levels within each treatment group will also be provided.

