Helixmith Co., Ltd. Protocol VMDN-003b

CONFIDENTIAL

Page x of y <Version>

Table 14.2.2.2

Analysis of Responder Rate of at least a 50% Reduction from Baseline in Average 24-hour Pain Score by Study Visit and Treatment Tabulation of Fitted Summary Statistics from GLMM for Repeated Measures

ITT Population

Study Visit Statistic [1]	Placebo (N=XX)	VM202 (N=XX)
Day 90	7.07	
n	XX	XX
LS Mean Responder Rate (SE) (95% CI for LS Mean Responder Rate)	XX.X (X.XX) (XX.X, XX.X)	XX.X (X.XX) (XX.X, XX.X)
LS Mean Difference from Placebo (SE)		XX.X (X.XX)
(95% CI for Difference from Placebo)		(XX.X, XX.X)
P value for Difference from Placebo [2]		X.XXXX
Day 180		
n	XX	XX
LS Mean Responder Rate (SE)	XX.X (X.XX)	XX.X (X.XX)
(95% CI for LS Mean Responder Rate)	(XX.X, XX.X)	(XX.X, XX.X)
LS Mean Difference from Placebo (SE)		XX.X (X.XX)
(95% CI for Difference from Placebo)		(XX.X, XX.X)
P value for Difference from Placebo [2]		X.XXXX
Cont	inue for Day 270 and Day 365	

Abbreviation: CI = confidence interval; LS = least squares; SE = standard error.

Note: Subjects are summarized by randomized treatment. Subjects with a percent change of ≤ -50% from baseline (i.e., reduction of at least 50%) will be classified as a responder at the respective visit. The baseline value is the average 24-hour pain score from the diary collected prior to Day 0.

[1] Estimates for LS means and accompanying 95% CIs and P values are from a generalized linear mixed-effects model for repeated measures (GLMM) based on a logit link function. The model included treatment, visit, treatment-by-visit interaction, baseline use of gabapentin and/or pregabalin, and baseline average 24-hour pain scores as covariates. An unstructured covariance matrix was used to model the within subject correlation.

[2] P value for testing for difference in responder rate between treatments at the specified visit.

SOURCE: Listing 16.2.6.1

Programming note: Check convergence per Section 8.1 of the SAP. Other variance-covariance structures selected from among compound symmetry, Toeplitz, and autoregressive (1) options may be substituted if convergence problems arise. Update footnotes accordingly.

Table 14 2 2 3

Analysis of Responder Rate of at least 50% Reduction from Baseline in Average 24-hour Pain Score by Study Visit and Treatment Tabulation of Fitted Summary Statistics from GLMM for Repeated Measures using Multiple Imputation

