[1] Estimates for LS means and accompanying 95% CIs and P values are from a generalized linear mixed-effects model for repeated measures (GLMM) based on a logit link function. The model included treatment, visit, treatment-by-visit interaction, baseline use of gabapentin and/or pregabalin, baseline average 24-hour pain scores, HbA1c subgroup, and HbA1c-by-Treatment interaction as covariates. An unstructured covariance matrix was used to model the within subject correlation.

[2] P value for testing for difference in responder rate between baseline and the specified visit.

[3] P value for testing for difference in responder rate between treatments at the specified visit.

[4] P value for Gail and Simon test of no qualitative interaction

SOURCE: Listing 16.2.6.1

Programming note: Check convergence per Section 8.1 of the SAP. Other variance-covariance structures selected from among compound symmetry, Toeplitz, and autoregressive (1) options may be substituted if convergence problems arise. Update footnotes accordingly.

Table 14.2.2.7.4

Analysis of Responder Rate of at least 50% Reduction from Baseline in Average 24-hour Pain Score by Study Visit and Treatment Tabulation of Fitted Summary Statistics from GLMM for Repeated Measures with HbA1c Covariate

ITT Population

Same shell as 14.2.1.2.2. HbA1c as a covariate in the model and in footnote [1].

Table 14.2.2.8.1

Summary of Subjects with at least 50% Reduction from Baseline in Average 24-hour Pain Score by Gender ITT Population

Same shell as 14.2.1.2.1, add a row at the top of table reading "Group: Male". Once all records from group are summarized, update row text for the Female group and start table on a new page. Add 16.2.4 to SOURCE.

Table 14.2.2.8.2

Analysis of Responder Rate of at least 50% Reduction from Baseline in Average 24-hour Pain Score by Study Visit, Treatment, and Gender Tabulation of Fitted Summary Statistics from GLMM for Repeated Measures

ITT Population

Same shell as 14.2.1.2.2, add a row at the top of table reading "Group: Male". Once all records from group are summarized, update row text for the Female group and start table on a new page. Add 16.2.4 to SOURCE.

Table 14.2.2.8.3

Analysis of Responder Rate of at least 50% Reduction from Baseline in Average 24-hour Pain Score by Study Visit and Treatment Tabulation of Fitted Summary Statistics from GLMM for Repeated Measures with Gender-by-Treatment Interaction ITT Population

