Table 14.2.3.2.1

Analysis of Responder Rate of at least a 20% Reduction from Baseline in Average 24-hour Pain Score by Study Visit and Treatment Tabulation of Fitted Summary Statistics from GLMM for Repeated Measures mITT Population

Study Visit Statistic [1]	Placebo (N=XX)	VM202 (N=XX)
Day 90		
n	XX	XX
LS Mean Change in Responder Rate from Baseline (SE) (95% CI for LS Mean Change in Responder Rate from Baseline)	(XX.X, XX.X)	XX.X (X.XX) (XX.X, XX.X)
LS Mean Difference from Placebo (SE) (95% CI for Difference from Placebo)		XX.X (X.XX) (XX.X, XX.X)
P value for Difference from Placebo [3]		X.XXXX
Day 180		
n	XX	XX
LS Mean Change in Responder Rate from Baseline (SE)	XX.X (X.XX)	XX.X (X.XX)
(95% CI for LS Mean Change in Responder Rate from Baseline)	(xx.x, xx.x)	(XX.X, XX.X)
LS Mean Difference from Placebo (SE)		XX.X (X.XX)
(95% CI for Difference from Placebo)		(XX.X, XX.X)
P value for Difference from Placebo [3]		X.XXXX
Continue for Day	270 and Day 365	

Abbreviation: CI = confidence interval; LS = least squares; GLMM = generalized linear mixed-effects model; SE = standard error.

Note: Subjects are summarized by randomized treatment.

The baseline value is the average 24-hour pain score from the diary collected prior to Day 0.

[1] Estimates for LS means (percent change from baseline) and accompanying 95% CIs are from a generalized linear mixed-effects model for repeated measures (GLMM) based on a logit link function. The model included treatment, visit, treatment-by-visit interaction, baseline use of gabapentin and/or pregabalin, and baseline average 24-hour pain scores as covariates. An unstructured covariance matrix was used to model the within subject correlation.

SOURCE: Listing 16.2.6.1

Programming note: Other variance-covariance structures selected from among compound symmetry, Toeplitz, and autoregressive (1) options may be substituted if convergence problems arise. Update footnotes accordingly.

Table 14.2.3.2.2

Analysis of Responder Rate of at least a 30% Reduction from Baseline in Average 24-hour Pain Score by Study Visit and Treatment Tabulation of Fitted Summary Statistics from GLMM for Repeated Measures mITT Population

Same shell as 14.2.3.2.1

Table 14.2.3.2.3

Analysis of Responder Rate of at least a 40% Reduction from Baseline in Average 24-hour Pain Score by Study Visit and Treatment Tabulation of Fitted Summary Statistics from GLMM for Repeated Measures mITT Population

Same shell as 14.2.3.2.1

Table 14.2.3.2.4

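### SAP 8.1 responder model: the covariance described does not match the code, and the coded output is logits under responder-rate labels

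*SAP*

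**What the plan says.** SAP 8.1 compares responder percentages with a logit-link mixed model for repeated measures over the 3, 6, 9 and 12 month visits. The text lists "baseline average 24-hour pain scores as covariates with an unstructured variance-covariance matrix". If convergence fails, "Other variance-covariance structures selected from among compound symmetry, Toeplitz, and autoregressive (1) options will be substituted based on the lowest AIC". Note [1] of Tables 14.2.2.2, 14.2.2.7.3 and 14.2.3.2.1 says "An unstructured covariance matrix was used to model the within subject correlation".

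The SAS code that follows is introduced as the code with which the analysis will be done. It uses PROC GLIMMIX with METHOD=QUAD, a binary distribution and a logit link. Its only covariance term is "random INTERCEPT / SUBJECT=usubjid type=un". Its LSMEANS line ends "trtp *avisitn / diff cl".

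The Table 14.2.2.2 shell heads its rows "LS Mean Responder Rate (SE") and, below that, a difference from placebo with its interval. Tables 14.2.2.7.3 and 14.2.3.2.1 use "LS Mean Change in Responder Rate from Baseline (SE") instead. Note [2] of Table 14.2.2.7.3 defines a "P value for testing for difference in responder rate between baseline and the specified visit".

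Two related items in SAP 8.1 concern the continuous analysis. The PROC MIXED statement carries a quadrature method, and the Day 270 to Day 365 arm comparison is to come from a contrast statement.

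**The concern.** A programmer who follows the code and a reader who trusts the table notes would hold different models in mind. The printed responder estimates would also be on a different scale from their labels.

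A negative rate would be noticed at programming. The real risk lies in what happens next. Someone would have to choose a covariance and a reporting scale once data are in hand, for a plan that SAP 1 describes as set in advance. SAP 13 exempts small changes to titles, footnotes and row order from a SAP revision; these choices go beyond that.

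The obvious patch, adding the ILINK option, would give numbers that look plausible but are still not the responder rates a reader would take them for.

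The model feeds 20 planned tables: 14.2.2.2 to 14.2.2.6 (5), the HbA1c, gender and age model tables (9), 14.2.2.13 (1) and 14.2.3.2.1 to 14.2.3.2.5 (5).

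**Working it through.** The documents give no responder rate, sample size or power for this model, so there is no figure to reproduce. Every rate, SD and sample size below is an assumption.

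**Covariance.** An unstructured matrix over k = 4 visits has k(k+1)/2 = 10 parameters, 6 of them correlations. The coded model has 1 variance. A 1 x 1 matrix is the same whether called unstructured, compound symmetric, Toeplitz or AR(1), so the AIC fallback has nothing to choose between. The code implies one equal latent-scale correlation between all pairs of visits, SD²/(SD² + π²/3): 0.23, 0.55 or 0.73 for an intercept SD of 1, 2 or 3.

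**Scale.** Assume population responder rates of 35% (VM202) and 20% (placebo), and a random-intercept SD s. Let baseline pain and gabapentinoid use add a logit spread of SD c. The quantity LSMEANS prints is the η that solves E[expit(η + b)] = rate, with b ~ N(0, s² + c²). Gauss-Hermite quadrature with 80 nodes gives:

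| s | c | VM202 row | Placebo row | Difference row |
|---|---|---|---|---|
| 0.5 | 0 | -0.655 | -1.459 | 0.804 |
| 1 | 0 | -0.746 | -1.650 | 0.903 |
| 2 | 0 | -1.016 | -2.228 | 1.212 |
| 3 | 0 | -1.339 | -2.929 | 1.590 |
| 3 | 0.6 | -1.36 | -2.97 | 1.61 |

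The shell labels call for 35.0, 20.0 and 15.0. The pooling code in SAP 6.1.4 combines estimates and standard errors without back-transforming them.

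**Would ILINK fix it?** No. It back-transforms each arm's mean but supplies no difference row, and the result is the rate for a subject whose random effect is zero. With c = 0, expit(-1.016) = 26.6% and expit(-2.228) = 9.7% at s = 2. At s = 3 the values are 20.8% and 5.1%. Neither pair matches the assumed 35% and 20%, and both would disagree with the observed percentages in Table 14.2.2.1.

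**Labels.** A 50% reduction from baseline cannot have occurred at baseline, so the baseline responder rate is zero by definition. The change-from-baseline rows therefore equal the visit rates. Note [1] of Table 14.2.3.2.1 gives the quantity a third name, a percentage change. The test that LSMEANS attaches to each mean is of a logit of zero, which is a rate of 50%. It is not the baseline comparison that note [2] of Table 14.2.2.7.3 describes.

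**Error rate of the coded model.** A simulation took visit-level logit SDs of 2 and 3 with AR(1) correlation 0.9, 0.8 and 0.6. It used 100 subjects per arm, 30% responders in both arms and 2,500 runs per setting. The Monte Carlo SE is √(0.05 × 0.95/2500) = 0.44 points.

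- Day 365 comparison: 5.1, 4.8 and 4.5% (SD 2); 4.8, 6.0 and 4.6% (SD 3).
- Day 270 to 365 comparison: 4.3, 3.4 and 4.3% (SD 2); 4.3, 4.4 and 3.5% (SD 3).

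The first set is near nominal. The second lies below 5% throughout, so it is slightly conservative.

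**Continuous analysis.** Quadrature is not an estimation method in PROC MIXED, so the statement would stop with an error and bias nothing. The MODEL and REPEATED lines agree with the text. For Day 270 to 365, no shell has a row for the model-based arm difference; Table 14.2.1.1.5 covers only change from baseline by visit. An unadjusted interval can still be formed from the n and SD per arm in Table 14.2.1.1.3. Its half-width is 1.96 × SD × √(2/n). For SD 1.5 and n = 100 per arm this is 0.42 points; for SD 2.0 and n = 50 it is 0.78.

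**The case against.** The covariance contradiction depends partly on a reading. The text never says what the matrix runs over, and in a mixed model it could be the random-effects matrix; the code does carry an unstructured option, and a random intercept does model within-subject correlation. This stands as a qualification. Visits remain the natural reading, because Toeplitz and AR(1) have meaning only across ordered occasions. What is firm on either reading is that the option and the fallback do nothing as coded.

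A reader might infer that the mismatch inflates the treatment effect, by setting the population odds ratio, (0.35/0.65)/(0.20/0.80) = 2.15, against larger subject-specific values. That does not follow. Population-averaged and subject-specific odds ratios differ under any correctly specified model, and the SAP plans no population-averaged fit. The values exp(1.212) = 3.36 and exp(1.590) = 4.90 are consequences of the assumed SDs, not results of fitting a visit-level model.

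A reader might also infer that the Day 270 to 365 comparison would have no estimate or interval. A CONTRAST statement alone does give only a test. But SAP 8.1 states that estimates are the aim, and SAP 4.1 commits to 95% confidence intervals for tests. Only the absent table row is firm.

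Finally, with a baseline rate of zero, the change-from-baseline label is redundant more than false. That is fair for the row label, but it does not rescue the p-value attached to it.

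**Conclusion.** The point holds. Followed as printed, the responder model's description and code disagree, its rows carry logits and log odds ratios under rate labels, and one planned p-value does not test what it claims. The printed ranges rest on the assumed 35% and 20%, an intercept SD of 0.5 to 3 and a covariate spread of 0 to 0.6; the scale error itself needs none of these.

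Severity is minor to moderate. Responder status is not among the endpoints in Protocol 5.6.2 or SAP 2.2, and Protocol 5.6.3 calls the analyses descriptive only. The observed counts in Tables 14.2.2.1 and 14.2.3.1 are unaffected. The missing back-transformation does not alter the visit-wise treatment p-values. The covariance choice can move them, but on the simulation the coded model's error rate is near nominal at Day 365 and mildly conservative for Day 270 to 365. The documents do not support a claim that the tests are invalid or that a primary result is at risk.

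Misdirected shell cross-references are not counted, because SAP 13.1 makes table numbers placeholders.

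**What to change.** Before any unblinded analysis of the extension data:

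1. State the random-intercept logistic model in SAP 8.1 and the table notes, and delete the unstructured and fallback wording for this model.
2. Report the arm comparison as an odds ratio with 95% confidence interval and relabel the rows. If rates are wanted, specify population-averaged rates and differences, with a stated variance method and a rule for pooling over the ten imputed datasets.
3. Relabel the change-from-baseline responder rows as visit results on the chosen scale, correct note [1] of Table 14.2.3.2.1, and delete the baseline p-value in Table 14.2.2.7.3.
4. Replace the quadrature method in PROC MIXED with REML.
5. Add a row for the model-based Day 270 to 365 arm difference, (VM202 365 - 270) minus (placebo 365 - 270), with its estimate and 95% confidence interval from ESTIMATE or LSMESTIMATE.

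The cost is SAP wording, code and shells, with no new data. Keeping the random intercept is the cheapest route and, on the simulation, costs little in error control. A visit-level covariance is harder to justify for sparse binary data. A residual-side version cannot be fitted with METHOD=QUAD and offers no comparable AIC, and a GEE fit would need a stronger missing-data assumption. Population-averaged rates add programming time.

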8.2. Daily Pain Diary Subgroup Analysis

The daily pain diary data will be analyzed within the below subgroups:

- Baseline HbA1c (< and ≥ median)
- Gender (male and female)
- Age (<65 years and > 65 years).

For baseline HbA1c, the median will be the VMDN-003 median and subjects will be summarized within the same group as that study. For each subgroup of the ITT population, the

change in average 24-hour pain score will be summarized by treatment group and visit using descriptive statistics including mean, median, standard deviation, minimum, and maximum. The count and percentage of subjects with a change in the average 24-hour pain score will also be summarized by treatment group and visit for each subgroup of the ITT population. Both types of descriptive summaries are also provided for the subgroups of baseline use of gabapentin and/or pregabalin, study center, and VMDN-003 protocol version the subject enrolled under.

Except for the subgroups of study center and protocol version, the Repeated Measures Model analyses described in Section 8.1 will be performed within each subgroup.

A sensitivity analysis excluding subjects that took prohibited medications on more than 14 consecutive days will be presented also. Both types of descriptive summary statistics and efficacy models will be run with these subjects excluded.

Additionally, the possible treatment-by-subgroup interaction will be tested for each subgroup variable as follows:

- A subgroup variable will be included in the primary analysis models described in Section 8.1 along with its interaction with the treatment effect. If the p-value of the interaction term is ≥ 0.05, the treatment-by-subgroup interaction is not significant.
- If the interaction effect is statistically significant (i.e., p-value < 0.05), then the Gail and Simon test will be used to test for the qualitative interaction at a significance level of 0.05 and provided as an aid for interpretation.

The Repeated Measures Model analyses described in Section 8.1 already accounts for the subgroups of baseline use of gabapentin and/or pregabalin (i.e., Yes and No groups). For evaluating the interaction between treatment and baseline use of gabapentin and/or pregabalin, the interaction effect will be added to the primary analysis models. If the interaction effect is significant, then the Gail and Simon test will be used to test for the qualitative interaction at a significance level of 0.05.

8.3. Daily Sleep Interference Diary Analysis

The daily sleep interference diary data will be analyzed using the continuous Repeated Measures Model described in section 8.1. A descriptive summary will also be presented.

This data will also be listed.

8.4. Patient's Global Impression of Change (PGIC)

Patient's Global Impression of Change (PGIC) results will be summarized at Day 365. The change will be assessed relative to the VMDN-003 baseline. The results will be summarized by the following three categories:

- Very Much Improved or Much Improved
- Minimally Improved/Worsened or No Change

Much Worse or Very Much Worse

PGIC will be analyzed by Cochran-Mantel-Haenszel (CMH) test to account for the stratification variable and row means scores differ statistic (row variable: treatment group, column variable: 3-category data of PGIC) will be used.

PGIC results will be listed.

Efficacy data will be summarized by treatment group and by treatment group within baseline gabapentin and pregabalin use.

9. Safety and Tolerability Analysis

Safety assessments will be collected at the Day 365 visit and include adverse events, concomitant medications, and vital signs.

All safety analyses will be performed on the safety population by actual treatment received in the VMDN-003 study.

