4.4. PATIENT'S GLOBAL IMPRESSION OF CHANGE (PGIC)

The patient's global impression of change after treatment will be measured using the Patient's Global Impression of Change (PGIC) questionnaire. This questionnaire measures a patient's perception of how treatment has affected their level of activity, symptoms, emotions, and overall quality of life. Each descriptor is ranked on an intensity scale of 1 = Very Much Improved; 2 = Much Improved; 3 = Minimally Improved; 4 = No Change; 5 = Minimally Worse; 6 = Much Worse 7 = Very Much Worse. This test will be self-administered during study visits on Day 365.

Upon completion of the questionnaire, the study coordinator will check the questionnaire for completeness. Any omissions or ambiguous answers will be clarified by the subject prior to leaving the clinic. The PGIC can be found in Appendix 3. Note, the subject will be required to initial and date the PGIC.

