5.6.2. SECONDARY ENDPOINTS

The secondary efficacy endpoints are:

- 1. The change in the average 24-hour pain score from baseline to the Day 365 follow-up from the Daily Pain and Sleep Interference Diary;
- 2. The change in the average 24-hour pain score from Day 270 to the Day 365 follow-up from the Daily Pain and Sleep Interference Diary; and
- 3. Patient's Global Impression of Change (PGIC) at the Day 365 follow-up.

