Analysis of Responder Rate of at least a 60% Reduction from Baseline in Average 24-hour Pain Score by Study Visit and Treatment Tabulation of Fitted Summary Statistics from GLMM for Repeated Measures mITT Population

Same shell as 14.2.3.2.1

Table 14.2.3.2.5

Analysis of Responder Rate of at least a 70% Reduction from Baseline in Average 24-hour Pain Score by Study Visit and Treatment Tabulation of Fitted Summary Statistics from GLMM for Repeated Measures mITT Population

Same shell as 14.2.3.2.1

Table 14.2.4.1 Summary of Change from Baseline in Average 24-hour Sleep Score ITT Population

Same shell as Table 14.2.1.1.1.

Table 14.2.4.2

Summary of Change from Baseline in Average 24-hour Sleep Score by Gabapentin and/or Pregabalin use at Baseline ITT Population

Same shell as Table 14.2.4.1, add a row at the top of table reading "Group: Gabapentin and/or Pregabalin Use". Once all records from group are summarized, update row text to "Group: No Gabapentin and/or Pregabalin Use" and start table on a new page.

Table 14.2.4.3
Summary of Change from Day 270 Average 24-hour Sleep Score
ITT Population

Same shell as Table 14.2.4.1, only include Day 270 and Day 365 timepoints. Update headers from 'CFB' to 'CFD270' and '%CFD270'. Drop the [1] footnote.

Update abbreviation footnote to say CFD270 = change from day 270 visit.

[figure not shown]
Table 14.2.4.4
Summary of Change from Day 270 Average 24-hour Sleep Score by Gabapentin and/or Pregabalin use at Baseline ITT Population

Same shell as Table 14.2.4.3, add a row at the top of table reading "Group: Gabapentin and/or Pregabalin Use". Once all records from group are summarized, update row text to "Group: No Gabapentin and/or Pregabalin Use" and start table on a new page.

Table 14.2.4.5

Mean Change from Baseline in Average 24-hour Sleep Score by Study Visit and Treatment
Tabulation of Fitted Summary Statistics from MMRM
ITT Population

Same shell as 14.2.1.1.4

Helixmith Co., Ltd. Protocol VMDN-003b

CONFIDENTIAL

Page x of y <Version>

Table 14.2.5.1
Summary of Patient's Global Impression of Change (PGIC)
ITT Population

Study Visit Statistic	Placebo (N=XX) n (%)	VM202 (N=XX) n (%)
Day 365		
1: Very Much Improved or Much Improved	XX (XX.X%)	XX (XX.X%)
0: Minimally Improved/Worsened or No Change	XX (XX.X%)	XX (XX.X%)
-1: Much Worse or Very Much Worse	XX (XX.X%)	XX (XX.X%)
P value [1]	XX (XX.X%)	XX (XX.X%)

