Note: The denominator for percentage corresponds to the N in each column. N is the number of subjects in the safety population. Subjects are summarized by treatment received in the VMDN-003 study.

[1] P-value from a Cochran-Mantel-Haenszel (CMH) test (stratified by baseline use of gabapentin/pregabalin) comparing VM202 to Placebo. SOURCE: Listing 16.2.6.2

[figure not shown]
[figure not shown]

Table 14.2.5.2
Summary of Patient's Global Impression of Change (PGIC) by Gabapentin and/or Pregabalin use at Baseline mITT Population

Same shell as Table 14.2.5.1, add a row at the top of table reading "Group: Gabapentin and/or Pregabalin Use". Once all records from group are summarized, update row text to "Group: No Gabapentin and/or Pregabalin Use" and start table on a new page. Do not include the CMH test or footnote.

Helixmith Co., Ltd. Protocol VMDN-003b

CONFIDENTIAL

Page x of y <Version>

Table 14.3.1.1.1 Summary of Treatment Emergent Adverse Events Safety Population

Category	Placebo (N=XX) n (%)	VM202 (N=XX) n (%)	Overall (N=XX) n (%)
Subjects with at least one TEAE	XX (XX.X%)	XX (XX.X%)	XX (XX.X%)
Subjects with at least one TEAE related to study medication	XX (XX.X%)	XX (XX.X%)	XX (XX.X%)
Subjects with at least one TEAE related to injection procedure	XX (XX.X%)	XX (XX.X%)	XX (XX.X%)
Subjects with at least one TEAE leading to discontinuation	XX (XX.X%)	XX (XX.X%)	XX (XX.X%)
Subjects with at least one TEAE leading to death	XX (XX.X%)	XX (XX.X%)	XX (XX.X%)
Subjects with at least one SAE	XX (XX.X%)	XX (XX.X%)	XX (XX.X%)

Abbreviations: PT = Preferred Term; SOC = System Organ Class; TEAE = Treatment emergent adverse event; SAE = Serious treatment emergent adverse event; N = Number of subjects in the safety population; n = Number of subjects with events.

Note: The denominator for percentage corresponds to the N in each column. Subjects are summarized by treatment received in the VMDN-003 study. AEs were coded using MedDRA version 21.0. A TEAE is any AE that occurs after the last visit in the VMDN-003 study and pre-existing medical conditions that worsen following the last visit in the VMDN-003 study.

SOURCE: Listing 16.2.7.1

[figure not shown]
[figure not shown]

Table 14.3.1.1.2

Summary of Treatment Emergent Adverse Events by Gabapentin and/or Pregabalin use at Baseline Safety Population

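### PGIC is collapsed from seven levels to three before the CMH mean-score test, so the test and the summary tables cannot see movement, or its direction, among the three middle levels

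*SAP*

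**What the plan says.** - **Endpoint.** Protocol 5.6.2 lists "Patient's Global Impression of Change (PGIC) at the Day 365 follow-up" as the third secondary efficacy endpoint. SAP 2.2.2 repeats it.
- **Scale collected.** Protocol 4.4 describes seven ordered levels: "Each descriptor is ranked on an intensity scale of 1 = Very Much Improved; 2 = Much Improved; 3 = Minimally Improved", and so on to 7 for very much worse. The form in Protocol Appendix 4 has the same seven boxes.
- **Scale analysed.** SAP 8.4 forms three groups. The top two levels form one, the bottom two another, and the middle group is "Minimally Improved/Worsened or No Change".
- **Test.** SAP 8.4 specifies a CMH test in which the "row means scores differ statistic (row variable: treatment group, column variable: 3-category data of PGIC) will be used".
- **Scores and strata.** The shell for Table 14.2.5.1 labels the middle row "0: Minimally Improved/Worsened or No Change", with 1 and -1 for the outer groups. Its footnote reads "P-value from a Cochran-Mantel-Haenszel (CMH) test (stratified by baseline use of gabapentin/pregabalin) comparing VM202 to Placebo".
- **What remains at seven levels.** Only Listing 16.2.6.2, which prints each subject's overall status. Table 14.2.5.2 reuses the three-row shell without the test. No seven-level table or test is planned, and no reason for the grouping is given.

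**The concern.** The row-mean-scores statistic is made for ordered columns. It accepts seven levels as readily as three, with the same stratification, so the collapse is not needed to run it.

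The grouping gives one score to opposite directions of change. Two arms could differ clearly in how many subjects are slightly better rather than slightly worse, and the test and both PGIC tables would show no difference. The study's second objective is durability of effect, and a fading benefit could appear first as drift through exactly these middle levels. What is at stake is the sensitivity and direction of one of three secondary efficacy endpoints, in a study whose size is not planned.

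**Working it through.** **Inputs from the documents.** Seven ordered levels (Protocol 4.4). Three-category scores 1, 0, -1 (SAP Table 14.2.5.1). Two-sided 0.05 (SAP 4.1). SAP 3.2 states no sample size or power, and neither document gives a PGIC distribution or effect size, so there is no plan figure to reproduce.

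**Assumptions.** Nine control-arm distributions, a common odds ratio from 1.2 to 2.5, 1:1 allocation, strata ignored, and 100 per arm where power is shown. None of these comes from the documents.

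**Formulas.** Let p and q be the control and VM202 proportions over the seven levels, m = (p + q)/2, and s the scores.
- Mean difference d = Σ s(q − p); pooled variance v = Σ s²m − (Σ s m)²; efficiency e = d²/v.
- Relative efficiency = e(three categories) / e(seven levels). It does not depend on sample size.
- z = √(n e/2) for n per arm; power ≈ Φ(z − 1.96).
- Seven-level scores are 3, 2, 1, 0, −1, −2, −3, equivalent to 1 to 7 reversed. Three-category scores on the same levels are 1, 1, 0, 0, 0, −1, −1.

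**Step 1: movement within the middle.** Levels 3, 4 and 5 all score 0. Moving any share of subjects among them leaves d = 0, whatever the distribution. This needs no assumption.

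**Step 2: one proportional-odds case in full.** Control 5/15/25/35/12/6/2%, odds ratio 1.8. For example, the top-two cumulative share of 0.20 has odds 0.25; 0.25 × 1.8 = 0.45, and 0.45/1.45 = 0.310. The VM202 distribution becomes 8.65/22.38/28.52/28.25/7.59/3.49/1.12%.
- Seven levels: d = 0.413, v = 1.690, e = 0.101.
- Three categories: d = 0.144, v = 0.281, e = 0.074.
- Relative efficiency 0.0740/0.1011 = 0.73, a loss of 27%.
- At 100 per arm: z = 2.25 against 1.92, power 61% against 49%.

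**Step 3: all nine assumed distributions.**

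| Control distribution, levels 1 to 7 (%) | Loss over OR 1.2 to 2.5 | Power at OR 1.8, 100 per arm: seven vs three |
|---|---|---|
| 15/25/8/15/7/20/10 (bimodal) | 9–10% | 63% vs 59% |
| Equal shares | 10–11% | 65% vs 60% |
| 12/28/25/22/7/4/2 | 12–14% | 61% vs 55% |
| 10/25/30/25/6/3/1 | 13–18% | 61% vs 54% |
| 5/15/10/55/5/7/3 | 15–18% | 57% vs 50% |
| 20/35/22/15/5/2/1 | 15–19% | 59% vs 51% |
| 5/15/25/35/12/6/2 | 24–30% | 61% vs 49% |
| 2/8/25/40/17/6/2 | 43–48% | 60% vs 37% |
| 1/4/25/45/20/4/1 | 64–67% | 58% vs 24% |

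With ridit scores or the proportional-odds information as the seven-level comparator, the full range is about 9% to 69%.

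**Step 4: effects that are not proportional odds.** Same control distribution as in Step 2, 10 percentage points moved, 100 per arm.
- *Minimally worse* to *minimally improved*: seven levels d = 0.20, v = 1.590, z = 1.12; three categories z = 0.
- *Minimally improved* to *much improved*: seven levels d = 0.10, v = 1.788, z = 0.53; three categories d = 0.10, v = 0.301, z = 1.29. The three-category test is about 5.9 times as efficient here, and about 5 to 7 times across the nine distributions.

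**The case against.** The strongest reply is that the two tests ask different questions. The three-category test asks about at least much change; the seven-level test asks about average shift. Step 4 shows that the first wins clearly when benefit consists only of moving subjects across the boundary between minimally and much improved. This stands. A reader might infer that the grouping gives up power for nothing, and that would be wrong. It is a reason to keep the three-category result, but not to have it alone and unexplained.

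A reader might also infer a definite loss, such as 15% to 33%. The documents cannot support that, because any such figure depends on an assumed distribution and on proportional odds.

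Three further limits stand:
- Protocol 5.6.2 names PGIC without fixing an analysis scale, so the SAP does not contradict it.
- Individual responses survive in Listing 16.2.6.2; the loss is in the test and the summary tables.
- The grouping is pre-specified, so there is no inflation of type I error.

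It can also be said that Protocol 5.6.3 calls the analyses descriptive only and that the study is unpowered. That limits the consequences but does not remove the point. The SAP plans this p-value, and if description is the purpose, the tables are where direction of change is hidden.

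**Conclusion.** The point holds in a bounded form. It is certain from the text that three of the seven levels, including opposite directions of change, share one score, and that neither the test nor any planned PGIC table can separate them. The size is illustrative only: roughly 10% to 45% loss of efficiency under proportional odds for most of the distributions tried, and about two thirds when nearly all responses lie in the middle. Every proportional-odds case tried showed a loss; an effect confined to the minimally/much boundary reverses it. These figures rest on assumed distributions, 1:1 allocation and no strata. It is a worthwhile and cheap improvement to a secondary endpoint. It does not threaten the validity of the study.

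**What to change.** Amend SAP 8.4 before unblinding:
1. Apply the CMH row-mean-scores test, stratified by baseline gabapentin/pregabalin use, to the seven-level PGIC, stating the scores in advance (integer or modified ridit).
2. Show all seven levels in Tables 14.2.5.1 and 14.2.5.2.
3. Keep the three-category summary and its test as a supportive analysis of at least much change, with the reason for the grouping stated.

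No new data are needed. The cost is a short SAP edit, a few table rows and one extra p-value, and the three-category p-value becomes supportive. If unblinding has already taken place, the seven-level test can still be reported, labelled as unplanned, as SAP section 1 requires for such analyses.
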